3.4.3. Intent-to-Treat-c (ITT-c)

The Intent-to-Treat (ITT-c) Population includes all subjects in the SAF Population with their SARS-CoV-2 status confirmed by central RT-PCR viral load at baseline \geq lower limit of quantification (LLOQ) and with at least one post-baseline primary efficacy measurement. Subjects will be analyzed as randomized.

The reasons for exclusion from the ITT-c population will be summarized by treatment group using the Safety population.

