2.1. Overall Study Design and Plan

This is a randomized, double-blind, placebo-controlled, parallel group, multi-site study in non-hospitalized adult subjects who test positive for SARS-CoV-2 and have COVID-19 symptom onset within 5 days of randomization and who are not at high risk for progression to severe COVID-19. Subjects can be vaccinated or unvaccinated for COVID-19. Subjects with prior COVID-19 infection <90 days before enrollment and/or who received a COVID-19 vaccine dose <90 days before enrollment are excluded from trial participation.

[figure not shown]
Subjects will be randomized in a 1:1:1 ratio to receive either EDP 235 [REDACTED], EDP 235 [REDACTED], or placebo orally once daily for 5 days. Randomization will be stratified by age (≤ 50 years or 51 to 64 years) and by the duration of COVID-19 symptoms (≤ 3 days or >3 days and ≤ 5 days).

The study includes 4 periods:

- Screening period will occur from Day -1 to Day 1. Screening should be completed as soon as possible, and the subject will be randomized within 24 hours of signing the ICF. A subject will be considered enrolled at the time of randomization.
- Treatment period will begin with the first dose of study treatment on Day 1 and will conclude with the end-of-treatment (EOT) visit on Day 5.
- Follow-up period will begin following the last dose of study treatment and will conclude at the end of follow-up (EOFU) visit on Day 33 (28 days after the last dose of study treatment).
- Long-term follow-up period (LTFU) will begin at Day 34 and concludes at the end-of-study (EOS) visit at Week 24.

An overview of the study design is shown in **Figure 1**. Study site visits and assessments are detailed in the Schedule of Study Procedures ([Appendix 14.1](#)).

Figure 1: Study Design

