7.4. Electrocardiogram

All Electrocardiogram (ECG) results will be summarized by treatment group and visit in the Safety population and a listing will be presented of all results with abnormalities flagged.

8. Efficacy Analysis

Unless otherwise specified, efficacy analyses will be performed using ITT-c population and the following methods will be implemented:

For time to event endpoints time and date will be used and 24 hours will be considered as a day. Descriptive statistics using the Kaplan-Meier method will include the median, 25th percentile, and 95% CIs (log-negative-log transformation). Additionally, the cumulative event rate (SE) will be summarized by treatment group and presented graphically over time. For between group comparisons, Cox Proportional Hazards models (tie handling will be addressed first using the exact method then with Efron's method if the exact method does not converge) will include treatment group, randomization stratification factors of age (≤ 50 years or 51 to 64 years) and duration of COVID-19 symptoms (≤ 3 days or >3 days and ≤ 5 days), and the baseline value of the endpoint. The hazard ratios with associated 95% CIs (Wald) and p-values (analysis of maximum likelihood estimates) comparing EDP 235 [REDACTED] versus Placebo, and EDP 235 [REDACTED] versus Placebo will be reported. Model assumptions will be checked via a log-negative-log plot and/or Schoenfeld residuals as appropriate. Subjects who do not achieve the specified endpoint will be censored with time imputed as treatment start time as follows:

COVID-19 diary:

- Subjects who have not been followed through the Day 33 visit (discontinuation from study or incomplete follow-up at the time of analysis) or completed Day 33 diary will be censored at Day 33.

Other time to event endpoints:

- Subjects who discontinued from the study will be censored at Day 33.
- Subjects who have completed the Day 33 visit will be censored at Day 33 Visit Date.

For treatment comparisons of change from baseline endpoints, analysis of covariance (ANCOVA) models will include treatment group, randomization stratification factors of age (≤ 50 years or 51 to 64 years) and duration of COVID-19 symptoms (≤ 3 days or >3 days and ≤ 5 days) and baseline value of the endpoint as the covariate. The least-squares means, SE, and 95% CIs will be presented for individual groups and the difference between groups. The p-value for

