8.1. Primary Efficacy Endpoints

The primary efficacy endpoints are as follows:

- Time to improvement of targeted COVID-19 signs/symptoms using the COVID-19 Symptom Diary through Day 33
- Time to SARS-CoV-2 RNA Viral Load TND Assessed by RT-qPCR

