8.2. Secondary Efficacy Endpoints

8.2.1. Proportion of Subjects with Targeted COVID-19 Signs/Symptom Improvement using the COVID-19 Symptom Diary through Day 33

The proportion of subjects demonstrating targeted COVID-19 signs/symptoms improvement through Day 33 will be summarized overall and by treatment group and CMH methods applied as described in [Section 8](#).

8.2.2. Change from Baseline in Targeted COVID-19 Signs/Symptom Total Score using the COVID-19 Symptom Diary through Day 33

Change from baseline in targeted COVID-19 signs/symptoms will be summarized for the total mean score and analyzed using the methods described in [Section 8](#).

Additionally, the 14 individual symptom scores will be summarized descriptively by study visit for each treatment group.

8.2.3. Proportion of Subjects with Medically Attended Visits for COVID-19 Through Day 33

The proportion of subjects with medically attended visits for COVID-19 through Day 33 will be summarized by treatment group and will be analyzed using the same CMH methods as described in [Section 8](#).

8.2.4. Proportion of Subjects Requiring Hospitalization (Defined as ≥ 24 Hours of Acute Care) for COVID-19 Through Day 33

The proportion of subjects requiring hospitalization for COVID-19 through Day 33 will be summarized by treatment group by treatment group and will be analyzed using the same CMH methods as described in [Section 8](#).

8.2.5. Proportion of Subjects who Require Hospitalization and Mechanical Ventilation (Invasive and Non-Invasive) Through Day 33

The proportion of subjects who require hospitalization and mechanical ventilation through Day 33 will be summarized by treatment group and will be analyzed using the same CMH methods as described in [Section 8](#).

8.2.6. Proportion of Subjects with COVID-19 Related Events or All-Cause Mortality Through Day 33

COVID-19 related events include complications based on the investigator's assessment, medically attended visits, hospitalizations, intensive care unit (ICU) admissions, requirement for supplemental oxygen or increased in supplemental oxygen requirement, requirement for mechanical ventilation (invasive and non-invasive) or all-cause mortality. The proportion of subjects with COVID-19 related events or all-cause mortality through Day 33 will be summarized by treatment group and will be analyzed using the same CMH methods as described in [Section 8](#).

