8.2.7. Change from Baseline in SARS-CoV-2 RNA Viral Load Assessed by RT-qPCR Through Day 33

The antiviral activity of EDP 235 on viral kinetics will be measured using SARS-CoV-2 RNA viral load assessed by RT-qPCR of NP swab samples on Days 1, 3, 5, 9, 14, and 33. Change from baseline values for SARS-CoV-2 RNA viral load will be summarized using the methods described in [Section 8](#).

8.2.8. Change from Baseline in Infectious SARS-CoV-2 Viral Load Assessed by Cell Culture Infectivity Assay Through Day 33

The infectious SARS-CoV-2 viral load will be measured using a SARS-CoV-2 cell culture infectivity assay of NP swab samples on Days 1, 3, 5, 9, 14 and 33. Change from baseline values for infectious SARS-CoV-2 viral load will be summarized using the methods described in [Section 8](#).

8.2.9. AUC of SARS-CoV-2 RNA Viral Load Assessed by RT-qPCR Through Day 33

The area under the curves (AUC) from Day 1 through Day 33 will be calculated for SARS-CoV-2 viral load data using actual sampling times via non-compartmental analysis using Phoenix[®] WinNonlin[®] Version 8.3.4 or higher according to the linear trapezoidal with linear interpolation

8.3.4. AUC of SARS-CoV-2 RNAemia Viral Load Through Day 33

The area under the curve (AUC) from Day 1 through Day 33 will be calculated for SARS-CoV-2 RNAemia viral load data using actual sampling times via non-compartmental analysis using Phoenix® WinNonlin® Version 8.3.4 or higher according to the linear trapezoidal with linear interpolation. AUCs will be derived for Days 1-14 and Days 1-33. Additionally, the AUC from Day 1 through Day 14 and the AUC from Day 1 through Day 33 will be standardized for 14 and 33 days by multiplying $14, 33/t_{last}$ where t_{last} is the actual time in days of the last available assessment. No AUC values will be calculated if there are less than 3 results available. The same methods used in [Section 8.2.9](#) will be applied.

8.3.5. Time to SARS-CoV-2 RNAemia TND Through Day 33

Time to SARS-CoV-2 RNAemia to TND is defined as per [Section 8.1.1.2](#) and will be summarized and analyzed as described in [Section 8](#).

8.3.6. Change from Baseline in SARS-CoV-2 Nucleocapsid Antigenemia Through Day 33

Change from baseline of SARS-CoV-2 nucleocapsid antigenemia will be summarized as described in [Section 8](#).

8.3.7. Proportion of Subjects with Positive SARS-CoV-2 Serostatus at Day 33

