| Clinical laboratory assessments (chemistry, hematology, coagulation) | | X ^{d*} | | X | | X | | X | | X | | X ^g | | | | *Blood samples for select laboratory assessments should be taken from all randomized subjects and sent to the local laboratory for these identified tests (noted with superscript “a” in Protocol Table 1), which should be assayed and reported in an expedited manner. Review of laboratory results is not required prior to randomization or dosing. In parallel, hematology, chemistry, and coagulation panels should be sent to the central laboratory with the other Day 1 samples. From D1 through D5, samples should be collected predose. See Protocol Section 1.4 for the list of laboratory assessments. |
| Follicle stimulating hormone | | X ^d | | | | | | | | | | | | | | Follicle-stimulating hormone should be tested in selected postmenopausal females. Protocol Section 8.1.6 |
| 12-lead ECG (resting) | | X ^d | | | | X | | | X | | | X ^g | | | | Protocol Section 8.3.2 |
| COVID-19 Symptom Diary | X | X ^d | X | X | X | X | X | X | X | X | X | X | X | | | The COVID-19 Symptom Diary will be completed by participants during Screening to determine eligibility and after randomization, predose on Day 1 as a baseline measurement. If Screening and Day 1 occur on the same calendar day, the Screening Diary entry will be used as the baseline measurement and a separate Day 1 Diary will not be collected. In addition, the diary will be completed once daily at the same time each day ±2 hours. Protocol Section 8.2.2 |
| Global Impression Questions | | X ^d | X | X | X | X | X | X | X | X | X | X | X | X ^h | | Global impression questions include Return to Usual Health, Return to Usual Activities, PGI-C and PGI-S questions, which will be answered every day from D 1 to D33 after the COVID-19 |

| Period | SCR | Treatment | | Follow-up ^a | | | | | | | | LT Follow-up | Notes | | |

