|---------------------------------------------------------------------------|-----|-------------------------|--------------------------------------------------------------------------------|------------------------|----|------------------|------------------|------------------|-------------------|------------------|--------------------------------|------------------|------------------|------------------|------------------------------------------------------------------------------------------------------------------------------------------------------------------------------------------------------|
| | | 1 ^c Rand. | 2 | 3 | 4 | 5 ^e | 6 to 8 | 9 (±1d) | 10 to 13 (±1d) | 14 (±1d) | 15 to 32 (±1d) ^e | | | 33 (±7d) | Wk 12 (±7d) |
| Visit Name | SCR | V1 | T1 | V2 | T2 | EOT | V3 | V4 | V5 | V6 | EOFU | V7 | V8 | EOS | |
| Type of Visit | C | C | T | C/H ^f | T | C/H ^f | C/H ^f | C/H ^f | C/H ^f | C/H ^f | C/H ^f | C/H ^f | C/H ^f | C/H ^f | |
| | | | | | | | | | | | | | | | |
| EQ-5D-5L | | X ^d | | | | X | | | X | | X | | | X ^h | |
| NP swabs collection | | X ^d | | X | | X | | X | X | | X | X | | X | |
| SARS-CoV-2 serology sample collection | | X ^d | | | | | | | | | X | | | | |
| [REDACTED] | | | | | | | | | | | | | | | |
| Study staff review of COVID-19 Symptom Diary and other PRO questionnaires | | | Continuous from baseline through Day 33 | | | | | | | | | | | | Protocol Section 8.1.7 |
| Assess ICU admissions, hospitalizations, and medically attended visits | | | Continuous from randomization through end of study participation | | | | | | | | | | | | Medically attended visits include any unscheduled interactions with healthcare professionals other than study staff or designees that are not for routine health maintenance. Protocol Section 8.2.3 |
| Adverse events | | | Continuous from signing of ICF through end of study participation ⁱ | | | | | | | | | | | | Protocol Section 8.4 |
| Concomitant medications and therapies | | | Continuous from signing of ICF through end of study participation | | | | | | | | | | | | Concomitant medications and therapies will include the use of supplemental oxygen, increased |

| Period | SCR | Treatment | | Follow-up ^a | | | | | | LT Follow-up | | Notes | | |

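### Sections 8.2.3 to 8.2.6 default to ITT-c, so a treated, baseline-confirmed subject with an early event but no post-baseline diary entry or swab drops out of the endpoints that count that event (rare)

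*SAP*

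**What the plan says.** The opening of Section 8 sets the default: "Unless otherwise specified, efficacy analyses will be performed using ITT-c population". Section 3.4.3 builds ITT-c from the Safety Population. It requires a central RT-PCR viral load at or above LLOQ at baseline, "and with at least one post-baseline primary efficacy measurement".

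Section 8.1 introduces two endpoints with "The primary efficacy endpoints are as follows": time to symptom improvement from the diary, and time to RNA target not detected by RT-qPCR. The qualifying measurement is therefore a post-baseline diary entry or a post-baseline RNA viral load.

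Sections 8.2.3 to 8.2.6 refer to Section 8 for their CMH methods and name no population. Section 8.2.6, for example, says: "The proportion of subjects with COVID-19 related events or all-cause mortality through Day 33 will be summarized by treatment group".

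In the schedule (Section 14.1.1), ICU admissions, hospitalisations and medically attended visits are collected "Continuous from randomization through end of study participation". Adverse events, oxygen use and mechanical ventilation are collected from consent onwards.

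**The concern.** A post-baseline diary entry or swab is needed to compute the diary and viral-load endpoints. It is not needed to know whether a subject was hospitalised, ventilated or died, because those events have their own continuous collection. For these four endpoints the condition is a post-randomisation exclusion that can depend on the outcome being counted: an early death or severe deterioration can itself be the reason why no diary entry or swab was ever given.

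At stake are the proportions, risk differences and CMH tests of four secondary endpoints, one of which includes all-cause mortality. Where events are few, a single omission matters most.

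**Working it through.** **Text check**

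1. Population: Section 8 defaults to ITT-c, and Sections 8.2.3 to 8.2.6 specify nothing else, so ITT-c applies.
2. Entry to ITT-c: treated, baseline viral load at or above LLOQ, and at least one post-baseline diary entry or RNA result (Sections 3.4.3 and 8.1). There is no exception for subjects who die or are hospitalised first. The SAP does not define a primary efficacy measurement separately. Diary or swab is the lenient reading; requiring both would exclude more subjects.
3. Timing: the Day 1 diary and swab are predose baselines. The schedule says "the diary will be completed once daily at the same time each day", so the first post-baseline entry is due on Day 2. Section 8.2.7 has viral load "assessed by RT-qPCR of NP swab samples on Days 1, 3, 5, 9, 14, and 33", so the first scheduled post-baseline swab is on Day 3.
4. Other analyses: the only planned sensitivity population is PP (Section 8.1.2). It is a subset of ITT-c and covers only the primary endpoints, so it does not bring the subject back.

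**Size, by illustration**

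The SAP has no figure to reproduce. Arm size n (50, 75, 100) and events k (1 to 3) are assumptions.

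One subject with an event is omitted: the proportion goes from k/n to (k−1)/(n−1).

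| n | k = 1 | k = 2 | k = 3 | Drop, points |
|---|---|---|---|---|
| 50 | 2.00% to 0.00% | 4.00% to 2.04% | 6.00% to 4.08% | 2.00, 1.96, 1.92 |
| 75 | 1.33% to 0.00% | 2.67% to 1.35% | 4.00% to 2.70% | 1.33, 1.32, 1.30 |
| 100 | 1.00% to 0.00% | 2.00% to 1.01% | 3.00% to 2.02% | 1.00, 0.99, 0.98 |

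**What the fix can cost**

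One subject of unknown status is counted as a non-event (k/n) rather than left out (k/(n−1)). The difference is k/(n(n−1)):

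- n = 50: 1/2450 = 0.041 points to 3/2450 = 0.122 points.
- n = 100: 1/9900 = 0.010 points to 3/9900 = 0.030 points.

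If that subject did have an event, the proportion is too low by 1/n: 2.00 points at n = 50 and 1.00 at n = 100.

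**The case against.** The strongest objection is materiality. The subject must be dosed, be confirmed at baseline, have an event, and then never give one diary entry or swab through Day 33. Section 2.1 enrols subjects "who are not at high risk for progression to severe COVID-19". The diary is daily and five post-baseline swabs are scheduled. Visits may be done at home, worsening during follow-up prompts an extra swab, and subjects who leave the study early are asked back for end-of-follow-up procedures (Section 14.1.1, footnotes a, e and f). One later entry or swab keeps the subject in. For medically attended visits alone (8.2.3) the case is close to empty. All of this stands, and it limits the point to a minor one. Section 8.2.3 still belongs with the others because its visits also feed the composite in 8.2.6.

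Second, the event is not hidden. Section 7.1.9 already plans a CMH comparison of serious adverse events through Week 24, and Section 7 puts safety analyses on the Safety Population. Deaths are tabulated under Section 7.1.2, reasons for ITT-c exclusion are summarised by arm, and listings cover all randomised subjects by default. This is true, but serious adverse events are a different endpoint, and none of these outputs puts the subject back into the proportions of 8.2.3 to 8.2.6.

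Third, removing the condition also brings in plain early dropouts of unknown status. Counting one of them wrongly as a non-event costs 1.0 to 2.0 points under the same assumptions, as much as the omission being repaired, and the SAP does not show which group is larger. That is a real cost. It is why incomplete follow-up should be reported by arm and the ITT-c result kept alongside. The rule does fit the general convention in Section 3 that percentages use all subjects in the analysis set.

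**Conclusion.** The concern holds as a minor, optional improvement. As written, a known early death or hospitalisation can be left out of the proportion meant to count it, and no other planned analysis restores it. If that happens once, the affected arm's proportion falls by 0.98 to 2.00 points for an assumed 50 to 100 subjects and 1 to 3 events per arm; with a single event it falls to zero. How likely this is cannot be derived from the SAP, and none is claimed beyond its being rare.

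The endpoints are secondary and have no multiplicity control, so no study conclusion is expected to turn on this. The conclusion rests on reading the required measurement as a diary entry or an RNA viral load, as Section 8.1 implies.

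**What to change.** Add to Sections 8.2.3 to 8.2.6:

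- The analysis set is all treated subjects with baseline central RT-PCR viral load at or above LLOQ, analysed as randomised, without the post-baseline measurement condition.
- All of them stay in the denominator. Those with no recorded event through Day 33 count as non-events, including those of unknown status.
- The number with incomplete follow-up to Day 33 is reported by arm.
- The analysis is repeated on ITT-c as a sensitivity analysis.

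Leave the ITT-c definition and the time-to-event rules unchanged.

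The cost is a short SAP addition, one population flag, one count row by arm and one repeat run, with no new data. The drawbacks are slightly different denominators across secondary endpoints and an explicit non-event assumption, which the count of incomplete follow-up lets the reader judge.

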3.4.4. Per Protocol (PP)

The Per Protocol (PP) Population includes all subjects in the ITT-c Population who do not have any protocol deviations that may unduly influence the primary efficacy outcomes as assessed by the sponsor prior to unblinding ([Section 4.2](#)) and do not meet any of the criteria shown below.

1. Compliance rate <80% ([Section 6.4.1. Extent of Treatment Exposure and Compliance](#))
2. Do not complete Day 33 Visit (discontinuation from study prior to Day 33 or incomplete follow-up at the time of analysis)

The reasons for exclusion from the PP Population will be summarized by treatment group and listed using the ITT-c Population.

Subjects will be analyzed in the treatment group that corresponds to the study treatment received during the study.

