8.1.1. Primary Analyses

8.1.1.1. Time to Improvement of Targeted COVID-19 Signs/Symptoms using the COVID-19 Symptom Diary through Day 33

Improvement of targeted COVID-19 signs/symptoms is defined by the following the event occurring on the first of 2 consecutive days or on Day 33 when the following criteria are met:

- All symptoms scored as mild, moderate or severe at baseline are scored as mild or absent
- All symptoms scored as absent at baseline are scored as absent

Time to improvement of targeted COVID-19 signs/symptoms through Day 33 will be summarized graphically using Kaplan-Meier plots and analyzed by the Cox proportional hazard model as described in [Section 8](#).

8.1.1.2. Time to SARS-CoV-2 RNA Viral Load TND Assessed by RT-qPCR through Day 33

Time to SARS-CoV-2 RNA to TND is defined as the time between the date of the first dose to the first date of achieving viral load TND.

Time to SARS-CoV-2 RNA TND will be analyzed as described in [Section 8](#).

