8.1.2. Sensitivity Analyses

The primary analyses above will be conducted on the PP population as a sensitivity analyses.

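### The per-protocol set drops every subject who misses Day 33, even with the event already recorded, so the only visible sensitivity analysis of the primary efficacy endpoints is selected on later attendance

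*SAP*

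**What the plan says.** SAP Section 3.4.4 builds the PP set from ITT-c. It takes out subjects with influential protocol deviations and keeps only those who "do not meet any of the criteria shown below". Criterion 1 is compliance below 80%. Criterion 2 is "Do not complete Day 33 Visit (discontinuation from study prior to Day 33 or incomplete follow-up at the time of analysis". Nothing in the section exempts a subject whose event was observed before leaving.

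Section 8.1.2 reads: "The primary analyses above will be conducted on the PP population as a sensitivity analyses". The visible text names no other sensitivity analysis for these endpoints.

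Both endpoints can be settled before Day 33. Section 8.1.1.1 counts improvement as "occurring on the first of 2 consecutive days or on Day 33 when the following criteria are met". Section 8.1.1.2 ends the clock at "the first date of achieving viral load TND", with no confirmatory sample. Section 8.2.7 describes "RT-qPCR of NP swab samples on Days 1, 3, 5, 9, 14, and 33", so four of the five post-baseline swabs precede Day 33.

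For subjects without an event, Section 8 gives the diary censoring rule for "Subjects who have not been followed through the Day 33 visit (discontinuation from study or incomplete follow-up at the time of analysis": they are censored at Day 33. For the other time-to-event endpoints, subjects who discontinue are also censored at Day 33.

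**The concern.** Take a fully compliant subject who improves on Day 7, is TND on Day 9 and then misses the Day 33 visit. Neither primary efficacy outcome is missing, yet the subject leaves the PP set. A subject who leaves on Day 15 still unwell goes too, although 14 event-free days were observed. Adherence is already covered by criterion 1 and the deviation screen. What criterion 2 adds is selection on attendance after, or instead of, the event. Kaplan-Meier and Cox methods are designed to use such partial follow-up.

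Section 4.1 lists adverse event, withdrawal by subject, physician decision and death among the reasons for leaving, and these may be related to arm or course. If unimproved subjects leave one arm more often, deleting them flatters that arm. If improved subjects leave it more often, deleting them penalises it. The main analysis carries event-free dropouts to Day 33 and the PP repeat deletes them, so no planned analysis uses their follow-up as it was observed.

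**Working it through.** The visible SAP states no sample size, event count or dropout rate, so there is no planned figure to reproduce. That criterion 2 deletes subjects with observed events follows from the text. Only the size needs assumptions.

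**Assumptions, set A.** One active arm against placebo; exponential time to improvement; placebo median 10 days; leavers have last contact on Day 14; Cox model with treatment only; 400,000 simulated subjects per arm to suppress sampling noise. Dropout depends on arm and on improvement by Day 14, not otherwise on the future event time.

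- A1: true HR 1.0; 30% of active subjects not improved by Day 14 leave, 5% of all others.
- A2: true HR 1.3; 20% of active subjects not improved by Day 14 leave, 5% of all others.
- A3: true HR 1.3; 15% of improved active subjects leave, 5% of all others.

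| Rule | A1 (true 1.0) | A2 (true 1.3) | A3 (true 1.3) |
|---|---|---|---|
| PP as written | 1.13 | 1.38 to 1.39 | 1.25 |
| Criterion 2 deleted, Day 33 censoring kept | 0.88 | 1.20 | 1.30 |
| Only subjects with an event exempted | 1.13 | 1.38 | 1.30 |
| All kept, censored at last contact | 1.00 | 1.30 | 1.30 |

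**Hand check of A1.** The proportion not improved by Day 14 is 2^(−14/10) = 0.379 in each arm. After deletion the active proportion is 0.379 × 0.70 / (0.379 × 0.70 + 0.621 × 0.95) = 0.265 / 0.855 = 0.310. Placebo stays at 0.379, because its 5% loss is even. The implied HR to Day 14 is ln(0.310)/ln(0.379) = 1.171/0.970 = 1.21. After Day 14 the remaining subjects have equal hazards, so the overall figure falls between 1.00 and 1.21, consistent with 1.13.

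**Subjects deleted, at an assumed 75 per arm.** Placebo loses 75 × 0.05 = 3.75 throughout.

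- A1, active: 75 × (0.379 × 0.30 + 0.621 × 0.05) = 10.9. Total about 15 of 150.
- A2, active: the proportion not improved is 2^(−1.3 × 1.4) = 0.283, so 75 × (0.283 × 0.20 + 0.717 × 0.05) = 6.9. Total about 11.
- A3, active: 75 × (0.717 × 0.15 + 0.283 × 0.05) = 9.1. Total about 13.

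**Milder dropout.** With 10% rather than 30% in A1, PP gives 1.02 against a true 1.0.

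**Assumptions, set B.** Continuous dropout; placebo median 7 or 12 days. A rate of 20% over 32 days is a daily hazard of −ln(0.80)/32 = 0.0070.

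| Dropout pattern | True HR | ITT-c, Day 33 censoring | PP | Last contact |
|---|---|---|---|---|
| 10%, both arms, unrelated to outcome | 1.0 | 1.00 | 1.00 | 1.00 |
| 20%, active only, before improvement | 1.0 | 0.86–0.87 | 1.06–1.08 | about 1.00 |
| 20%, active only, before improvement | 1.3 | 1.11–1.12 | 1.37–1.39 | about 1.30 |
| 20%, active only, after improvement | 1.0 | 1.00 | 0.92–0.94 | 1.00 |
| 20%, active only, after improvement | 1.3 | 1.30 | 1.21–1.23 | 1.30 |

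In the first row PP is unbiased but discards 7 to 8% of all observed events. Last-contact censoring recovers the truth in both sets because dropout was generated as independent of the future event time, given what had been observed.

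**The case against.** Any per-protocol set is selected on conduct after randomisation, and the compliance criterion is no exception. Day 33 is a scheduled visit at which both endpoints are still assessed, so requiring it is a recognisable convention. ITT-c is the main efficacy population and keeps every early event. PP exclusions are to be summarised by arm with reasons, so an imbalance would show. Section 8.1.2 does not say the PP repeat is meant to test dropout. All of this stands, and it limits the consequence. It does not explain why a subject with complete outcomes should be removed from a time-to-event analysis.

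A reader might infer that the PP repeat says nothing about robustness to dropout. That goes too far. When unimproved subjects leave, ITT-c and PP fall on opposite sides of the truth; when improved subjects leave, only PP moves. A gap between them would therefore be a signal, though it would not show which was nearer the truth.

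A reader might also infer that striking criterion 2 is enough. It is not. The PP repeat uses the rules of Section 8, so restored dropouts without an event would be censored at Day 33: A1 moves from 1.13 to 0.88 and A2 from about 1.38 to 1.20. Deletion alone cures only A3.

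The size is also open to challenge. A rate of 30% against 5% is extreme. At an assumed 75 per arm with no dropout, about 150 × (1 − 2^(−3.3)) = 135 events give a standard error of the log HR of about √(4/135) = 0.17, larger than ln 1.13 = 0.12.

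**Conclusion.** The point holds as a fault in how the sensitivity analysis is defined. Criterion 2 selects the PP set on attendance that may follow the event, and it discards observed events with certainty whenever a subject who has had the event misses Day 33. Bias arises only if dropout differs by arm and outcome. In the strongly unequal scenarios it moved the HR by about 0.05 to 0.13; with 10% against 5% it moved it by 0.02; with equal random dropout it did not move it. These figures rest on assumed rates and exponential times. "Only sensitivity analysis" refers to the visible text, since parts of the SAP are redacted.

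The documents do not support reading this as a defect in the main efficacy result, which uses ITT-c, or in the study's primary objective, which Table 1 gives as safety. The change is worth making because the PP repeat will be read as the check on the primary efficacy results and the correction needs no new data.

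**What to change.** For the time-to-event sensitivity analysis, amend Sections 3.4.4 and 8.1.2 before unblinding as follows:

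- Delete criterion 2; keep the compliance and deviation criteria.
- Count every event that a non-completer had before leaving.
- State explicitly that non-completers without an event are censored at their last diary entry (improvement) or last swab (TND), in place of the Day 33 rule in Section 8.
- Run the same last-assessment censoring on ITT-c. The main ITT-c result against this one shows the effect of censoring; this one against the revised PP result shows the effect of the adherence exclusions.

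Neither shortcut is enough. Deleting the criterion without the censoring change replaces one bias with another of opposite sign when unimproved subjects leave. Exempting only subjects with an event leaves A1 and A2 at 1.13 and 1.38.

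The cost is SAP wording, a changed population flag, a second censoring variable and one extra analysis. No new data are needed. The PP set is no longer a completer set, and last-assessment censoring still assumes that dropout is unrelated to the unobserved event time given what was observed.
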